2.5.3 Handling of intercurrent events

The imputation of missing data caused by intercurrent events will be handled by defining the estimand framework.

The primary estimand is described by the following four attributes:

1. The target population comprises Sickle Cell Disease Patients with Priapism.
2. The primary variable is percent reduction from baseline period in priapic events (priapism defined as unwanted, or painful erection lasting at least 60 min self-reported) by 26 weeks.
3. Treatment of interest: investigational drug will be a crizanlizumab solution provided every 4 weeks with an additional loading dose 2 weeks after the first dosing.
4. The intercurrent events are the events occurring after enrollment that may impact the treatment effect. The intercurrent events of interest are listed below:
 - a. Treatment discontinuation
 - b. Initiation or discontinuation of HU/HC or l-Glutamine (or other therapies to treat SCD and or to prevent/reduce VOCs such as voxelotor and erythropoietin) or of prophylactic treatment for priapism
 - c. Intake of analgesic (including opioids) or ad hoc transfusions administered temporarily
5. The summary measure is the median percentage change from baseline period in priapic events (priapism defined as unwanted, or painful erection lasting at least 60 min self-reported) by 26 weeks.

Handling of the intercurrent events:

The approach of accounting for intercurrent events is as follows:

- **For the intercurrent events 4a:** Only data before study treatment discontinuation will be included. The data between treatment discontinuation and week 26 will be imputed using Poisson distribution (primary method to handle missing data as described in [Section 2.5.4](#)).
- **For the intercurrent events 4b:** Only data before initiation or discontinuation of HU/HC or L-Glutamine (or other therapies to treat SCD and or to prevent/reduce VOCs such as Voxelotor and erythropoietin) or of prophylactic treatment for priapism will be included. The data between initiation or discontinuation of therapies to treat SCD or of prophylactic treatment for priapism and week 26 will be imputed using Poisson distribution (primary method to handle missing data as described in [Section 2.5.4](#)).
- **For the intercurrent events 4c:** Data after intake of analgesic (including opioids) or ad hoc transfusions administered temporarily will be included (treatment policy strategy).

2.5.4 Handling of missing values not related to intercurrent event

The missing values will be imputed for the primary analysis.

Missing values will be imputed using Poisson distribution, assuming the same effect as observed data. Imputed datasets (approximately 1,000) will be created, and each dataset will be analyzed using the method described for primary endpoint. The results will be combined using Rubin's rule ([Barnard J and Rubin DB 1999](#)).

Further details are mentioned in the [Section 5.4.1](#).

2.5.5 Sensitivity analyses

Sensitivity analysis 1: Tipping point analysis

To explore the robustness of analysis, sensitivity analysis as a 'tipping point approach will be performed for the primary endpoint to evaluate the impact of a deviation from the MAR assumption. The basic idea is to first impute the missing values using the multiple imputation (MI) method based on the missing at random (MAR) assumption, then adjusted by a delta value. The delta adjusting approach described in [Ratitch et al \(2013\)](#) will be used to find the tipping point, in a spectrum of conservative missing not at random (MNAR) assumptions, at which conclusions change from being favorable to being unfavorable. After such a tipping point is determined, clinical judgment can be applied as to the plausibility of the assumptions underlying this tipping point. Note that, tipping point analysis will be performed if there are significant number of missing data.

Further details are provided in [Section 5.4.1](#).

Sensitivity analysis 2

As part of the sensitivity analysis, treatment policy strategy (that is, data after the intercurrent events will be included) will also be applied for the intercurrent events 4a and 4b, described in [Section 2.5.3](#).

Note: Handling of intercurrent event 4c and missing data not related to intercurrent event will be same as described for the primary analysis.

Sensitivity analysis 3: Observed case analysis

As part of the sensitivity analysis, the primary analysis will be analyzed on all subjects in FAS without missing data.

Sensitivity analysis 4: For COVID 19 impact

Additionally, as the study is ongoing during COVID 19 pandemic, the impact of COVID-19 (if any) on the primary endpoint will be assessed in accordance to FDA's guideline entitled "Statistical Considerations for Clinical Trials During the COVID-19 Public Health Emergency". The analysis (as stated below) will be repeated on the FAS excluding the subjects with missing data due to COVID-19.

Percent reduction from baseline in priapic events will be tested using a nonparametric test (i.e., Wilcoxon's Sign Rank test). Hodges-Lehmann estimate of median percent reduction in priapic events will also be reported, along with corresponding 95% confidence intervals.

2.5.6 Supportive analyses

The supportive analyses described below will be performed on all FAS patients who have completed 26 weeks on treatment. Missing values will be imputed as stated in [Section 2.5.4](#)

Supportive analysis 1:

Annualized priapic Events Rate: The annualized rate of priapic events is defined as the total number of priapic events for a subject occurring from the date of initial infusion to the last contact date of the Treatment Phase of the study \times 365.25 divided by the number of days during that same time period. This calculation accounts for early dropouts or lost to follow-up by extrapolating the priapism events rate of every subject to 1 year.

Supportive analysis 2:

Percent reduction from baseline in priapic events will also be assessed by Week 52. Assuming uniformity in the occurrence of priapic events before exposure to crizanlizumab treatment, baseline will be adjusted for 52 weeks for analysis purpose.

Baseline (adjusted for 52 weeks): Number of priapic events in 12 weeks screening period \times (52/12) and percentage change from baseline = (Post baseline value – Baseline (adjusted to 52 weeks) value) \times 100 / Baseline (adjusted to 52 weeks) value.

Percentage reduction from baseline is the negative percentage change from baseline.

Supportive analysis 3:

The total number of priapic episodes in the screening period (12 weeks baseline) will be compared to the total number of priapic episodes occurring in the first 12 weeks on treatment (0-12 weeks) using a nonparametric test (i.e. Wilcoxon's Sign Rank test). Additionally, a similar analysis will be performed to compare to the total number of priapic episodes occurring in the last 12 weeks on treatment (15-26 weeks). For the analysis purpose, for 0-12 weeks: Day 1 to Day 84 and for 15-26 weeks: Day 105 to Day 182 will be used.

Supportive analysis 4:

Number of priapic events will be summarized in the screening period (12 weeks baseline), in first 12 weeks on treatment (0-12 weeks), and in the last 12 weeks on treatment (15-26 weeks) and percent reduction from baseline will also be summarized. For the analysis purpose, for 0-12 weeks: Day 1 to Day 84 and for 15-26 weeks: Day 105 to Day 182 will be used.

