##### **Supportive analyses**

- The supportive analyses described below will be performed on all FAS subjects who have completed 26 weeks on treatment. Missing values will be imputed as stated in [Section 12.4.3](#).Annualized priapic Events Rate: The annualized rate of priapic events is defined as the total number of priapic events for a subject occurring from the date of initial infusion to the last contact date of the Treatment Phase of the study  $\times$  365.25 divided by the number of days during that same time period. This calculation accounts for early dropouts or lost to follow-up by extrapolating the priapism events rate of every subject to 1 year.

- Percent reduction from baseline in priapic events will also be assessed by Week 52.
- The total number of priapic episodes in the screening period (12 weeks baseline) will be compared to the total number of priapic episodes occurring in the first 12 weeks on treatment (0-12 weeks) using a nonparametric test (i.e. Wilcoxon's Sign Rank test). Additionally, a similar analysis will be performed to compare to the total number of priapic episodes occurring in the last 12 weeks on treatment (15-26 weeks).
- Number of priapic events will be summarized in the screening period (12 weeks baseline), in first 12 weeks on treatment (0-12 weeks), and in the last 12 weeks on treatment (15-26 weeks) and percent reduction from baseline will also be summarized.

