2.1.1 General definitions

Study treatment: Study treatment refers to Crizanlizumab (SEG101) 5.0 mg/kg provided by IV infusion.

Study treatment start and end date: Study treatment start date is defined as the first date when a non-zero dose of study drug is administered and recorded on the Drug Administration Record (DAR) CRF page. Similarly, study drug end date is defined as the last date when a non-zero dose of study drug is administered and recorded on the DAR CRF page of the core study.

Baseline: Baseline period is defined as 12 weeks screening period prior to the first infusion of crizanlizumab 5 mg/kg at Week 1 Day 1.

- For the analysis purpose, in the tables and figures, baseline is considered from Day -91 to one day prior to dosing. Similarly, for "by week 26 analysis" from the first dose date to one day prior to Week 27 Day 1 visit date and for "by week 52 analysis" from the first dose date to one day prior to Week 53 Day 1 visit date will be considered.
- For subjects missing "Week 27 Day 1" visit or "Week 53 Day 1" visit, the scheduled visit day will be considered for cut-off.
- For listings, all available data will be considered.

For safety evaluations, the last available assessment on or before the date of start of study treatment is taken as "baseline" assessment. In case time of assessment and time of treatment start is captured, the last available assessment before the treatment start date/time is used for baseline.

For safety parameters (e.g. ECGs), where study requires multiple replicates per time point, the average of these measurements will be calculated for baseline (if not already available in the database).

In cases where multiple measurements meet the baseline definition, with no further flag or label that can identify the chronological order, then the following rule should be applied: If values are from central and local laboratories, the value from central assessment should be considered as baseline. If multiple values are from the same laboratory (local or central) or collected for ECGs or vital signs, then the last entry should be considered as baseline.

If subjects have no value as defined above, the baseline result will be missing.

Post baseline: Any measurements taken after baseline will be considered as post-baseline measurements.

Change from baseline: Post baseline value – baseline value

Percent change from baseline: (Post baseline value – baseline value) *100/ Baseline value;
(relative change from baseline).

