2.13 Interim analysis

A formal interim analysis for this study is not planned and shall not be performed. For publication purposes, only descriptive data will be reported, as needed. Any decision on study continuation will not be based on these reports, as such no alpha adjustment will be needed.

The primary analysis of the study will be performed after the last subject has completed Week 26 visit or discontinued earlier. For this analysis, all subjects will have completed the assessments related to the primary, secondary [REDACTED] objectives including all variables outlined up to Week 26 and all available visit-based safety assessments. Separate SAP documentation will be prepared for this primary analysis if applicable.

3 Sample size calculation

A total of 34 evaluable subjects is required for the study to have approximately 80% power to detect at least 25% reduction in rates of priapic events (defined as an unwanted erection lasting at least 60 min reported via daily diary tool) with a mean baseline priapism event rate of 10.0 and standard deviation of the difference of 5.0, by 26 weeks.

The calculations were based on simulation with 5,000 repetitions (from Poisson distribution) using one-sample Wilcoxon's Signed-Rank Test and 2-sided $\alpha=0.05$.

Retaining the same above assumptions, robustness of the estimated sample size was also validated using a one-sample t test.

Assuming a 5% dropout rate, approximately 36 subjects will be enrolled in the study.

Recruitment of the required number of subjects with priapism will be challenging as the incidence of priapic events are sporadic and varies over time intervals. Also, in the absence of relevant clinical data on priapism, the expected reduction and higher variability in events rates have been conservatively assumed. The above expected 25% reduction in rates of priapic events from baseline is based on medical expert opinion and feedback. L-glutamine (EndariTM) was approved by the US FDA in July 2017 for the reduction of vaso-occlusive crises (VOCs), based on a 25% reduction. Since priapism is also considered to be a complicated VOC, the assumption was that the relative risk reduction of 25% (approved for VOC events), would be similar for priapism.

4 Change to protocol specified analyses

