5.4 Statistical models

5.4.1 Analysis supporting primary objective(s)

Primary analysis

Wilcoxon signed rank test

The SAS procedure PROC UNIVARIATE will be used to perform Wilcoxon signed-rank test.

Hodges-Lehmann Estimation

The SAS procedure PROC NPAR1WAY will be used to compute the Hodges-Lehmann estimate.

Handling of missing data

Generating the multiple imputation

The missing values will be imputed for the primary analysis.

- To fill in the missing values (i.e. number of priapic events by 26 weeks), generate Poisson distributed random variables with a rate parameter based on the same effect as observed data. Compute 1000 such complete datasets. Use seed 10105.
- Each datasets will be analyzed using the same method as described in primary analysis.

Analyzing the imputed data

- The resulting estimates and standard errors will be combined using Rubin's rule ([Barnard J and Rubin DB 1999](#)), by the SAS procedure MIANALYZE.

Tipping point analysis for priapic events by 26 weeks

As a sensitivity analysis to evaluate the impact of missing data, a tipping point analysis will be performed for the primary endpoint.

The primary endpoint will be re-analyzed on the delta-adjusted datasets to see if the conclusions change. If not, a larger delta is chosen and the process will be repeated until the conclusion is overturned. The tipping point is the delta value which will cause the primary endpoint to be no longer statistically significant. A series of analyses on a range of delta values (i.e., 1,2,3,.....) will be performed to find the tipping point.

For each delta value, the following steps will be performed.

1. Impute the missing values (i.e. number of priapic events by 26 weeks) by generating Poisson distributed random variables with a rate parameter based on the same effect as observed data. Use seed 10105.
2. After the imputation obtained in above step, make the imputed value worse by a value of delta (i.e., add delta to the imputed value). Note: delta = 0 represents the standard missing at random (MAR).
3. The final imputed delta-adjusted dataset where all missing values are filled, will be analyzed using method as described in the primary analysis.

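### The Week 52 percent-reduction analysis (SAP 2.5.6, supportive analysis 2) uses a fixed 52-week baseline, but its imputation rules stop at Week 26, so Weeks 27 to 52 are left unfilled for a subject who stops

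*SAP*

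**What the plan says.** **Population.** SAP 2.5.6 opens: "The supportive analyses described below will be performed on all FAS patients who have completed 26 weeks on treatment". Protocol 12.4.4 sets the same population. SAP 2.2 and Protocol 12.1 carry a different general rule, which limits all efficacy analyses to FAS subjects who completed treatment. Planned treatment is up to 52 weeks (Protocol 6.1.4).

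**Endpoint.** Protocol 12.4.4 says only: "Percent reduction from baseline in priapic events will also be assessed by Week 52". SAP amendment 4 added that "baseline will be adjusted for 52 weeks for analysis purpose", using screening count x 52/12 for every subject. The post-baseline count runs from first dose to the day before the Week 53 visit. If that visit is missing, "the scheduled visit day will be considered for cut-off" (SAP 2.1.1).

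**Missing data.** The second sentence of SAP 2.5.6 refers to the imputation in 2.5.4: Poisson draws that assume the same effect as the observed data. The detail is elsewhere:
- SAP 5.4.1: "To fill in the missing values (i.e. number of priapic events by 26 weeks), generate Poisson distributed random variables".
- SAP 2.5.3, for treatment discontinuation: "The data between treatment discontinuation and week 26 will be imputed using Poisson distribution". Data after the stop are not used.

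**The concern.** Everyone who reaches Week 26 on treatment enters the analysis, including men who stop at any time in the following half year. Each is given a 52-week denominator. If his count ends when he stops and nothing is imputed afterwards, the weeks without data count as weeks without events.

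The error has one direction. Stopping, including for lack of effect or for toxicity, appears as benefit, and the sooner after Week 26 it happens, the larger the apparent benefit. This is the plan's 52-week percent-reduction analysis for all priapic events, so a reader could take it as evidence that the effect lasts.

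**Working it through.** **1. The plan's own figure.** The documents give no figure for the Week 52 analysis. The group size and event rate used below come from SAP 3: "A total of 34 evaluable subjects is required for the study to have approximately 80% power to detect at least 25% reduction", "with a mean baseline priapism event rate of 10.0 and standard deviation of the difference of 5.0, by 26 weeks". The difference is 10.0 x 0.25 = 2.5 with SD 5.0. A two-sided 0.05 one-sample t test has 80.8% power at n = 34 and 79.5% at n = 33. Dropout gives 34/0.95 = 35.8, so 36. The stated figures reproduce.

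**2. Does any rule fill Weeks 27 to 52?** Take a man who stops at Week 30.
- SAP 2.5.3 imputes from the stop to Week 26. For him that interval is empty.
- SAP 5.4.1 treats the 26-week count as the missing item. He completed 26 weeks on treatment.
- SAP 2.5.4 has no Week 26 limit in its own text, but its heading covers missing values not related to intercurrent events. Treatment discontinuation is intercurrent event 4a.

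So none of the rules, as written, reaches his Weeks 31 to 52.

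**3. One subject, no imputation after the stop.** With true reduction r and a stop at week w, the expected apparent reduction is 1 - (1 - r) x w/52.

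| Stop week | r = 0 | r = 25% |
|---|---|---|
| 26 | 50.0% | 62.5% |
| 30 | 42.3% | 56.7% |
| 39 | 25.0% | 43.8% |
| 45 | 13.5% | 35.1% |
| 51 | 1.9% | 26.4% |

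Example: 6 screening events give an adjusted baseline of 6 x 52/12 = 26. At the same rate (0.5 per week) he has 15 events by Week 30, and 1 - 15/26 = 42.3%. With the baseline scaled to observed time, 6 x 30/12 = 15 and the reduction is 0%.

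**4. The same subject under either repair.** Imputing Weeks w to 52 at his observed rate gives an expected reduction of 1 - (1 - r) x [w + (52 - w)]/52 = r. Scaling the baseline to w weeks gives 1 - (1 - r) x w/w = r. Both remove the artefact.

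**5. The group, n = 34, no drug effect, mean 10 events per 26 weeks.** Stop times are uniform over Weeks 26 to 52. Simulation A uses subject rates that vary, a baseline known without error, and the Hodges-Lehmann estimate. Simulation B uses a Poisson 12-week baseline that must be at least 3 (the entry rule), and the average median.

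| Share stopping | A: truncated minus complete | B: truncated minus no stoppers |
|---|---|---|
| 5% | 2.0 - 0.6 = 1.4 | not run |
| 10% | 2.5 - 0.5 = 2.0 | 9.6 - 7.4 = 2.2 |
| 20% | 5.4 - 0.6 = 4.8 | 11.8 - 7.4 = 4.4 |
| 30% | 7.8 - 0.7 = 7.1 | 13.9 - 7.4 = 6.5 |

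Ten percent of 34 is 3.4 men. Simulation A used three; a repeat with four gave 2.7. Rounded, the shifts are about 1, 2 to 3, 5 and 7 points. With imputation at each subject's own rate, A returns 0.5% to 0.8%, the same as with complete data. With the baseline scaled to observed time, B stays at about 7%.

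The 7.4% in B with no stoppers is an effect of entry selection and has nothing to do with stopping. At 20 events per 26 weeks, B moves from -1.9% with no stoppers to 3.2% at 20% stopping, a shift of 5.1 points, so the shift itself depends little on the event rate.

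**The case against.** A reader might infer that every man who stops after Week 26 will be credited with a false reduction of about 50%. The documents do not support that, for four reasons.

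- **Imputation is invoked.** SAP 2.5.6 applies 2.5.4 to all the supportive analyses. A programmer could reasonably carry the same method to the Week 52 horizon, and the artefact would then vanish. This stands as a possible reading, but the SAP does not say it, and the only horizon it states is Week 26.
- **The population is contested.** If the completed-treatment rule in SAP 2.2 means 52 weeks, the stoppers are excluded and the problem does not arise. The sentence in 2.5.6 is more specific and is repeated in the protocol, so the conflict is unresolved.
- **Counts need not end at the stop.** Protocol 8.2.1 asks for priapic events throughout the study, and Protocol 9.1.1 asks discontinued subjects to return for assessments where possible. However, the minimum data that 9.1.1 requires after a stop are treatments and adverse events, not priapic events. Truncation is therefore realistic but not automatic.
- **Other 52-week results adjust for exposure.** Supportive analysis 1 and the annualized rates in SAP 2.6.2 divide by each subject's own time. This limits the damage. It also shows that the sponsor allows for early stopping elsewhere and not in this analysis.

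**Conclusion.** The point holds in a conditional form. The rules as written leave Weeks 27 to 52 unfilled while charging every subject a 52-week baseline. If reporting ends at the stop and nobody extends the imputation, the result is biased toward benefit.

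The 50% is a ceiling for one no-effect subject stopping at exactly Week 26, not a group effect. The group shift is about 1 point at 5% stopping, the plan's only dropout figure, and about 7 points at 30%. These sizes rest on assumed stopping shares, uniform stop times, constant event rates and n = 34.

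A reader might also infer that trial success is at risk. It is not: success is judged at Week 26 under SAP 2.5.2, and the SAP names no significance test for supportive analysis 2. This should be corrected, but it does not touch the primary conclusion.

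**What to change.** In SAP 2.5.6, supportive analysis 2, adopt one of the following:
1. Replace the factor 52/12 by the subject's own time: baseline count x days observed / baseline days. Days observed run from first dose to the end of event collection or the intercurrent event, capped at Day 364.
2. State that the 2.5.3 and 5.4.1 imputation runs from the stop to Week 52 for this analysis.

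In addition, say whether the 26-week-completer population or the completed-treatment rule of SAP 2.2 governs the Week 52 analysis, and report beside the result the number of subjects who stopped between Weeks 27 and 52.

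The cost of option 1 is one SAP sentence and one line of programming before database lock; option 2 extends an existing procedure. Either option assumes a constant event rate over the year, and the Week 52 reduction may look smaller.

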**Figure 3-1 Study Design**

## 4 Rationale

### 4.1 Rationale for study design

The efficacy of crizanlizumab in SCD for the treatment of VOCs was established in the SUSTAIN study but was not fully investigated in priapism due to the limited number of cases observed during the study. The primary aim of this study is to demonstrate the clinical benefit of crizanlizumab in SCD-related priapism. A duration of 26 weeks was set to evaluate the primary efficacy of crizanlizumab on SCD-related priapism. This was based on studies conducted by Burnett and Olujohungbe, where recurrent ischemic priapic patients were evaluated over 16 and 26 weeks, respectively (Burnett et al 2014, Olujohungbe et al 2011). In addition, steady state concentrations for crizanlizumab were considered achieved by 15 weeks in the SEG101A2202 study.

The total duration of 52 weeks of treatment will enable evaluation of additional secondary [REDACTED] endpoints for the study.

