Visit-windows will be used for the data that is summarized by visit; they are based on the study evaluation schedule and comprise a set of days around the nominal visit day. For any assessment, there are the protocol defined scheduled visits around which visit windows were created to cover the complete range of days within the study. The visit windows are shown in Table 2-1. These apply to measurements taken at every visit.

When visit windows are used, all visits will be re-aligned, i.e., they will be mapped into one of the visit windows (e.g., if the Week 4 visit of a subject is delayed and occurs on Day 46 instead of on Day 29, say, it will be re-aligned to visit window Week 8). In the case of major deviations from the visit schedule, or due to unscheduled visits, several assessments of a subject may fall in a particular visit window (either scheduled or unscheduled). Statistical approaches to handle multiple assessments in a given visit window are specified below.

Table 2-1 Assessment windows for scheduled visits

Analysis Visit	Week (k)	Scheduled Day/ Target day [d=(k-1)*7+1]	Visit Window (in study days)
Baseline	BSL		-91 days to Day -1*
Week 1 Day 1	1	1	Day 1-7
Week 3 Day 1	3	15	Day 8-29
Week 7 Day 1	7	43	Day 30-57
Week 11 Day 1	11	71	Day 58-85
Week 15 Day 1	15	99	Day 86-113
Week 19 Day 1	19	127	Day 114-141
Week 23 Day 1	23	155	Day 142-169
Week 27 Day 1	27	183	Day 170-197
Week 31 Day 1	31	211	Day 198-225
Week 35 Day 1	35	239	Day 226-253
Week 39 Day 1	39	267	Day 254-281
Week 43 Day 1	43	295	Day 282-309
Week 47 Day 1	47	323	Day 310-337
Week 51 Day 1	51	351	Day 338-358
EoT	53	365	Day 359-371**

*Baseline measurement prior to first infusion of study drug.

**Based on medical judgement and data, upper limit of EoT will be extended upto maximum value day 447.

Laboratory assessments will be taken from Screening Visit 3 as per the protocol and the window does not include pre-screening period. Thus, window for laboratory assessments will be Day - 28 to Day -1.

Multiple assessments within visit windows

In order to summarize laboratory assessments over time (including unscheduled visits), the assessments will be time slotted. The following general rule will be applied:

- If more than one assessment is done within the same time window, the assessment performed closest to the target date will be used.
- If 2 assessments within a time window are equidistant from the target date, then the earlier of the 2 assessments will be used.

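### The SAP codes the weeks 15-26 window of Supportive analyses 3 and 4 as 78 days instead of 84 and compares it unscaled with baseline, which favours the drug on average

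*SAP*

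**What the plan says.** Supportive analysis 3 in SAP 2.5.6 sets the screening total against on-treatment totals: "The total number of priapic episodes in the screening period (12 weeks baseline) will be compared to the total number of priapic episodes" in the first 12 weeks, by signed-rank test. A similar comparison is planned with "the total number of priapic episodes occurring in the last 12 weeks on treatment (15-26 weeks"). Supportive analysis 4 summarizes counts and percent reduction for the same windows. Both paragraphs define the windows in study days. The early one is "for 0-12 weeks: Day 1 to Day 84". The late one is "for 15-26 weeks: Day 105 to Day 182 will be used".

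Protocol 12.4.4 gives the late window in weeks only: "in the last 12 weeks on treatment (15-26 weeks) and percent reduction from baseline will also be summarized". The study days therefore enter with the SAP.

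SAP Table 2-1 gives the rule that turns week k into a study day: "Scheduled Day/ Target day [d=(k-1)*7+1". It places Week 15 Day 1 on Day 99 and Week 27 Day 1 on Day 183.

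SAP 2.1.1 calls baseline the 12-week screening period, but for tables and figures it counts from Day -91 up to the day before dosing.

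**The concern.** The late window is labelled as 12 weeks, the same length as the baseline it is compared with, but its coded days make it shorter. Nothing in Supportive analyses 3 or 4 corrects for the difference. Elsewhere the SAP does adjust for unequal periods: the primary analysis multiplies baseline by 26/12 and Supportive analysis 2 multiplies it by 52/12. The lack of a factor here suggests that the windows were believed to be equal.

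A shorter on-treatment window lowers the expected on-treatment count and so produces an apparent reduction that is not due to treatment. The study has a single arm, so no control group would show the same artefact and reveal it. The late window is also likely to attract attention, because Protocol 4.1 states that "steady state concentrations for crizanlizumab were considered achieved by 15 weeks in the SEG101A2202 study".

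**Working it through.** **Inputs.** Window days: SAP 2.5.6. Week-to-day rule: SAP Table 2-1. Baseline counting days: SAP 2.1.1. Evaluable subjects (34) and planning rate (10.0): SAP section 3. Two-sided 5% level: SAP 2.1.

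**Step 1: window lengths** (last day - first day + 1).
- Early window: 84 - 1 + 1 = 84 days = 12 weeks. The stated length is reproduced.
- Late window as coded: 182 - 105 + 1 = 78 days = 11.14 weeks. The stated 12 weeks is not reproduced.
- Week 15 Day 1: (15 - 1) × 7 + 1 = Day 99. Week 26 ends the day before Week 27 Day 1, on Day 182. So weeks 15 to 26 are 182 - 99 + 1 = 84 days.
- Day 105 = 15 × 7 is the last day of week 15, so Days 99 to 104 (six days) are dropped.
- Reading the label as time after 15 completed weeks does not help: Day 106 to Day 182 is 77 days.

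**Step 2: expected apparent reduction with no drug effect** (1 - on-treatment days / baseline days).
- Late window as coded, 84-day baseline: 1 - 78/84 = 7.1%.
- Late window as coded, 91-day baseline (Day -91 to Day -1): 1 - 78/91 = 14.3%.
- Late window corrected to Day 99, 91-day baseline: 1 - 84/91 = 7.7%. The early window (84 days) carries the same 7.7%.
- Both windows 84 days: 0%.

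A true 25% reduction would appear as 1 - 0.75 × 78/84 = 30.4%, or 1 - 0.75 × 78/91 = 35.7%.

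**Step 3: effect on the signed-rank test.** No-effect trials were simulated with 34 subjects, the same true rate before and on treatment, and 2,000 replicates per case. The documents do not settle which period the rate of 10.0 covers, so the mean per 12 weeks is an assumption: 4.6 (10 × 12/26, if it is per 26 weeks), 10, and 20 as a high case. Each range spans Poisson counts with no between-subject variation and with gamma variation (CV 1). At mean 10 it also includes overdispersion matched to the planning SD of 5.0. Entries are the percentage of trials significant in the drug's favour (nominal 2.5%).

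| Mean per 12 weeks | 84 vs 84 days | 84 vs 78 days | 91 vs 84 days | 91 vs 78 days |
|---|---|---|---|---|
| 4.6 | 1.7-2.5 | 8.3-9.5 | 9.1-10.6 | 25.0-25.8 |
| 10 | 2.3-3.0 | 10.5-14.6 | 12.9-15.9 | 34.4-50.2 |
| 20 | 2.4-2.8 | 23.7-26.1 | 26.7-29.4 | 69.8-78.0 |

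Columns show baseline days, then on-treatment days. The entry requirement of at least 3 screening events was not imposed, so the table isolates window length.

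**The case against.** The strongest reply is that little depends on these analyses. SAP 2.5.2 ties success to the primary endpoint (a reduction of at least 25% with p < 0.05), which counts from first dose to the day before Week 27 Day 1 and scales baseline by 26/12. Supportive analysis 3 has no success rule and Supportive analysis 4 is descriptive. A 7.1-point artefact is also well short of 25%. All of this stands and limits the seriousness of the point.

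Four stronger readings are tempting but not supported:
- **That the analysis will show a reduction without any drug effect.** This is true only in expectation. Against an 84-day baseline, most simulated no-effect trials did not reach significance.
- **That every subject's count is lowered, always in the drug's favour.** A subject with no event on Days 99 to 104 loses nothing. Under Poisson counts that is exp(-4.6 × 6/84) = 72% of subjects at a mean of 4.6, and exp(-10 × 6/84) = 49% at a mean of 10. Protocol section 8 also allows Week 1 Day 1 to fall 7 days either side of its target, so screening can last about 77 to 91 days. For a 77-day screening period, a 78-day window is not the shorter one.
- **That this is the only steady-state efficacy analysis.** Protocol 4.1 uses the 15-week figure to support the 26-week duration. Neither document gives these analyses a steady-state purpose, and some sections are redacted.
- **That a growing effect over time would be claimed.** No test of the late window against the early one is planned. Analysis 4 shows them side by side, but how they would be read is conjecture.

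It could also be said that Table 2-1 governs scheduled visits, not event counting. But the early window and the Day 182 endpoint in SAP 2.5.6 both follow its rule. Only Day 105 departs from it.

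**Conclusion.** The coded window contradicts its own label and should be corrected. It is six days short. With raw totals compared, the late-window count is on average 7.1% too low against an 84-day baseline, and up to 14.3% too low if the Day -91 rule applies. In expectation this favours the drug. Against an 84-day baseline, favourable no-effect rejections rise from 2.5% to roughly 8% to 26%. Those rates are scenarios that rest on 34 subjects, Poisson-type counts and assumed means, not estimates for this trial. The window lengths and the expected percentages need only a constant event rate and the stated days.

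The consequence is confined to Supportive analyses 3 and 4. It does not put the primary conclusion or the sample size in doubt. Changing Day 105 alone would not be enough: if baseline is still counted from Day -91, up to 7.7% remains in both the late and the early comparison.

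**What to change.** In SAP 2.5.6, Supportive analyses 3 and 4, replace Day 105 to Day 182 with Day 99 to Day 182. For these two analyses, also state the baseline count explicitly: either count Day -84 to Day -1 (84 days), or divide each count by the days actually observed in its window. The second option also covers subjects whose screening was shorter than 84 days. Apply the same baseline rule to the Day 1 to Day 84 comparison.

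The cost is an edit to two SAP paragraphs and minor reprogramming, with no new data. The SAP history logs Amendment 4 as made before database lock. The downside for the sponsor is that the reported late-window reduction becomes slightly less favourable.
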